Efficacy evaluations: SALT, PGA, and Patient global assessment will be performed at every visit. PGA and patient evaluations will be based on similar 100mm visual analog scales. Patient quality of life assessments, performed at baseline, weeks 12, 24, 36, and 48, will be based on changes in the Dermatology Life Quality Index DLQI – adapted for hair loss, or the Dermatology Quality of Life Scales. Blood draws for safety assessments and immunology will be drawn at weeks 4, 12, 24 and 28(if needed for safety labs). Scalp biopsies for immunologic parameters will be obtained at baseline, and at one time point between weeks 4 and 20. Additional biopsies and blood draws may be obtained as clinically indicated. Since the timeline to regrowth may vary from subject to subject, unscheduled biopsies and blood draws will insure that tissue and blood samples are obtained at optimal timepoints to evaluate the changes occurring at the onset of growth or in the event of any unexpected clinical change. In addition, areas that are resistant to treatment may be biopsied to determine the cellular and immunologic differences of those areas compared to areas that are responding to treatment.

The patient will be given the option to agree to, or decline, the additional biopsies and blood draws.

Standardized photographs of the subject's scalp will be taken at Baseline, Week 4, 8, 12, 16, 20, 24, 36 and 48 and will be used to support determination of percent hair regrowth. Photography will consist of a high resolution digital camera mounted on a stereotactic arm. Patients will be positioned using a fixed guide after which photographs of the entire scalp will be taken at standardized locations and at a fixed distance. At a minimum, photographs of the crown, right and left lateral scalp and posterior scalp (views consistent with those used in the SALT measurement) will be taken.

Visit Schedule and Assessments

Screening assessments and all scheduled study visits are outlined in the Table of Study Assessments (please see below).

Informed consent

Written informed consent will be obtained from all patients for this study by the principal investigator or his/her designee prior to any protocol-specific procedures. The study will be conducted in accordance with the Food and Drug Administration (FDA) approved revision of the Declaration of Helsinki, current FDA regulations, and International Conference on Harmonization (ICH) guidelines.

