A 3-month interim analysis of the primary and secondary outcomes will be performed by an independent group in order to determine if statistical significance has been attained. A Haybittle-Peto rule for alpha spending (Haybittle 1971; Peto et al. 1976) will be followed for the interim analysis. If statistical evidence of efficacy is attained at 3 months and if the safety profile is acceptable, all patients will be offered the option of receiving open label active drug for the remaining duration of the trial.

To compare the frequency of occurrence of relapse in responders (followed for 6 months off therapy) across the four groups, we will employ a chi-squared test for comparing multiple proportions.

Furthermore, to compare the timing of relapse in responders (followed for 6 months off therapy) across the four groups, we will use tools from survival analysis (or, time-to-event analysis, with relapse as the event of interest). More specifically, first, we will conduct a descriptive analysis by graphically comparing the Kaplan-Meier survival (time-to-relapse) curves for the four groups. Next, we will use the log-rank test to formally test the null hypothesis of no difference between the survival functions of the four groups.

Specific Aim 2. To identify a clinical correlation between treatment outcome and down modulation of key AA-associated immunohistopathological markers and biomarkers in the treated skin; including NKG2DL expression in the hair follicle, immune infiltration (CD8⁺NKG2D⁺ cells) and expression of interferon response genes.

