Rationale Establishing the genetic basis of AA marks the beginning of rationally-designed mechanism-driven clinical research, but it is just the beginning. Very little is known about the immunopathogenesis of AA in humans. Rigorous clinical investigation of AA cannot be satisfied by mere clinical response evaluation. Indeed, our study will include longitudinal collection of AA biospecimens that will enable temporal assessment of biomarkers of patients (controls and treated) providing a unique resource to characterize the natural history of this disease. Given the budget constraints, our mechanistic studies in this Aim are focused on correlating treatment and disease status with; 1) histological improvement; 2) reduced IFN responses; 3) reduced HF NKG2DL expression; and 4) declines in circulating and peribulbar CD8⁺NKG2D⁺ infiltration. Previous studies in AA have reported elevated NKG2D expression in circulating CD8 T cells and NK cells³⁹, supporting the feasibility of our approach. Here we will be able to correlate the numbers of CD8⁺NKG2D⁺ cells in the blood with those infiltrating the target organ of patients with each other and as a function of disease status.

Procedures

i. Flow Cytometry Studies. The presence of CD8⁺NKG2D⁺ cells will be tracked in the blood and in the skin during treatment with IL TAC or vehicle. By assessing CD8⁺NKG2D⁺ involvement in longitudinally obtained skin biopsies we can correlate disease severity and clinical response (progression or regression) with immunopathological evidence of resolution of total cellular infiltration (by H&E) or loss of specific CD8⁺NKG2D⁺ cells in the skin (by IF) or in the blood (flow studies). CD8⁺NKG2D⁺ frequency in the peripheral circulation will be quantified using freshly isolated PBMCs obtained from 30 mls of blood obtained upon entry into the trial and at 4 wks, 12 wks and 24 wks during treatment. A portion of the PBMCs 2x10⁶ cells will be stained with anti-CD8, anti-CD25 and anti-NKG2D antibodies, stimulated with PMA/ionomycin in the presence of brefeldin and stained with anti-IFN- γ Abs. The remaining PBMCs will be viably frozen for future ancillary studies. We will seek evidence of a comparable pathogenic T cell subset in the human that we observed in C3H mice, namely an activated CD25⁺ IFN- γ producing CD8⁺NKG2D⁺ T cell.

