ii. Histology and Immunofluorescence Analysis. As shown in previous studies^{4,39} in active AA NKG2D ligands are upregulated on hair follicles in association with peribulbar NKG2D-bearing CD8⁺ T-cells and natural killer cells. We will seek evidence of resolution of total cellular infiltration (by H & E) and loss of specific CD8⁺NKG2D⁺ cells (by IF) and NKG2D ligands by comparing baseline biopsies with biopsies obtained on treatment after 4, 12, and 24 weeks. Frozen sections will be stained with anti-CD4, anti-CD8, anti-CD56 anti-NKG2D and anti-IFN- γ antibodies to visualize the total number of leukocytes, cytotoxic T-cells and NK cells present in the drug treated and placebo treated skin, respectively. Immunostaining with anti-ULBP3, anti-MICA antibodies and recombinant NKG2D soluble receptor (NKG2D-Ig, detects all NKG2D ligands, R & D systems) will determine whether NKG2DL “danger/stress” signals are down modulated with Jak1/Jak2 inhibition. Punch biopsies from patient skin before and after treatment will be embedded in OCT and 7-8 micron frozen sections will be cut. The sections will be fixed in 4% paraformaldehyde and stained overnight with primary antibodies for NKG2D ligands, receptor and immune markers. The following day, sections will be treated for 1 hr with fluorescence labeled antibody, counter-stained and mounted with DAPI containing media. Frozen sections will also be used to for H&E staining. The total number of immune cells, as well as NKG2D bearing cells, will be quantified by counting stained cells per magnification field using the NIH imaging software ImageJ and a student T-test will be carried out to determine significant changes in the number of infiltrating, NKG2D bearing T cells to correlate the simultaneous presence or absence of these cells in lesional skin and in circulation (by flow) during active disease or in remission.

iii. Analysis of Gene Expression by Quantitative RT-PCR

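### The only test named for Aim 2, a Student t-test on cell counts, cannot estimate the marker-outcome or skin-blood association, and the plan does not say whether it is paired

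*Combined protocol and SAP*

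**What the plan says.** The second of the protocol's two aims is worded "To identify a clinical correlation between treatment outcome and down modulation of key AA-associated immunohistopathological markers". The markers in question are interferon-related genes, the CD8+NKG2D+ infiltrate, and NKG2D ligands on the follicle.

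Three procedures follow.

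- **i. Flow Cytometry Studies** makes this claim for the serial samples: "we can correlate disease severity and clinical response (progression or regression) with immunopathological evidence of resolution of total cellular infiltration". It names no coefficient, regression or model.
- **ii. Histology and Immunofluorescence Analysis** sets baseline tissue against tissue taken during treatment, and for this "a student T-test will be carried out to determine significant changes in the number of infiltrating, NKG2D bearing T cells". The purpose given for the test is to relate the cells seen in skin to those seen in blood, by disease state.
- **iii. Analysis of Gene Expression by Quantitative RT-PCR** gives normalisation to a housekeeping gene and no test.

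The Data Analysis Plan gives ANOVA, pairwise comparisons and Bonferroni correction for secondary outcomes. Neither list of secondary outcomes contains a biomarker.

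On timing, the Efficacy evaluations paragraph says: "Scalp biopsies for immunologic parameters will be obtained at baseline, and at one time point between weeks 4 and 20". The Methods for Aim 1 and the visit list for weeks 4 to 20 agree with it, and a week 24 biopsy is optional. Aim 2 procedures ii and iii instead use weeks 4, 12 and 24.

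**The concern.** Aim 2 asks whether patients whose markers fall are the patients who regrow hair. A t-test on cell counts asks whether the mean count moved. These are different questions, and the second does not answer the first. The same sentence then gives the t-test a further task, relating skin to blood, which it also cannot do.

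The plan also leaves open whether the test is paired, which visits and arms it compares, and how several on-treatment biopsies would be handled. Aim 2 is one of only two specific aims. With four arms, several markers and investigator-chosen biopsy timing, an unspecified association analysis leaves wide room for choices made after the data are seen.

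**Working it through.** **1. The plan's own figure.** Aim 2 has no stated sample size, SD or effect size. The only power statement is for the four-group chi-squared test on responders. With N = 68, w = 0.4 and 3 degrees of freedom, the noncentrality is N·w² = 68 × 0.16 = 10.88 and power is 79.9% (stated: 80%). At w = 0.5 it is 68 × 0.25 = 17.0 and 94.8% (stated: about 95%). Both reproduce, but neither bears on Aim 2.

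**2. Does a test of change carry information on the correlation with outcome?** The paired statistic is t = mean(c) / (s_c/√n), where c is a patient's marker change. SALT does not enter it. Assume n = 68 with complete data and a mean change of 0.5 SD of the change. The noncentrality is 0.5 × √68 = 4.12 and power is 98%, whatever the correlation between c and SALT change. Simulation confirms this:

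| True correlation of change with outcome | Paired t-test rejects | Mean sample r |
|---|---|---|
| 0 | 98% | 0.01 |
| 0.6 | 98% | 0.60 |

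A two-sample t-test of baseline against on-treatment counts also leaves SALT out. The skin-blood correlation is missing for the same reason: blood counts do not enter a test on skin counts.

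**3. What a direct analysis could show.** By Fisher's z, SE = 1/√(n − 3).

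- With n = 68, SE = 1/√65 = 0.124. An observed r = 0.3 has z = 0.310 ± 1.96 × 0.124, giving a 95% CI of 0.07 to 0.50.
- The smallest r detectable with 80% power is tanh(2.80 × 0.124) = 0.33 with 68 patients, and tanh(2.80/√14) = 0.63 with 17.

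**4. What pairing could be worth.** The inputs are assumptions: a before/after shift of d = 0.6 SD, normal data, two-sided alpha 0.05, and within-patient correlation ρ from 0 to 0.7. Paired power uses a noncentral t with noncentrality d√n / √(2(1 − ρ)). For n = 17 and ρ = 0.5 this is 0.6 × 4.123 / 1 = 2.47 on 16 degrees of freedom, so power is 64%. The unpaired figures come from simulating the two-sample test on paired data.

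| ρ | n = 17 paired / unpaired | n = 51 paired / unpaired | True type I error of unpaired test, n = 17 |
|---|---|---|---|
| 0 | 38% / 40% | 84% / 85% | 5% |
| 0.3 | 50% / 38% | 94% / 89% | 2% |
| 0.5 | 64% / 36% | 99% / 93% | 0.8% |
| 0.7 | 85% / 34% | over 99% / 97% | 0.1% |

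Here 17 is one arm and 51 is the three active arms together (3 × 17). The plan does not say which applies.

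**5. Timing.** One biopsy between weeks 4 and 20 gives one pair per patient. Biopsies at weeks 4, 12 and 24 give repeated measures. These need different models, and the text supports both.

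**The case against.** The strongest reply is that the wording fits a paired test. The section speaks of change and says: "Punch biopsies from patient skin before and after treatment will be embedded in OCT". A Student t-test can be paired. This stands. A reader might infer that the plan ignores within-patient sampling, but the text does not support that: it leaves pairing unstated. The power loss then applies only to an unpaired reading. It is absent at correlation 0 and small with 51 patients. An unpaired test would also be conservative, so it would not create false positives. Biopsy sites may vary within a patient, so a low correlation cannot be excluded.

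Second, the t-test sits in one sub-procedure, the flow cytometry section separately promises correlation with clinical response, and the sentence ends by mentioning disease status. A t-test of marker change between responders and nonresponders would test an association. That is true, but the plan describes no such comparison, and the promise in the flow section comes with no method. Even that test would not give the skin-blood correlation.

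Third, a reader might add that cell counts are skewed and a t-test is therefore invalid. The documents give no count distribution, so this is not established.

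Finally, the trial calls itself a pilot, the Aim 2 work is limited by budget, and no biomarker is a primary or secondary outcome. This limits the importance of the point but does not remove it.

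**Conclusion.** The point holds as one about the match between aim and analysis. The only test named for Aim 2 is a test of mean change, with pairing unstated. In either form it estimates neither the marker-outcome association nor the skin-blood correlation, and no other section supplies a method. This conclusion needs no assumption about the data: outcome and blood counts do not enter the test.

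The power figures for pairing are illustrative. They rest on an assumed sample size, effect and within-patient correlation, none of which the documents give. The primary efficacy conclusion is unaffected. The plan should be corrected because the named analysis would leave one of its two aims unanswered, although data to answer it are planned.

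**What to change.** Replace the t-test sentence with a short analysis plan for Aim 2.

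- **Change.** Test within-patient change from baseline with a paired test, or with a mixed model with a patient effect if there are several on-treatment biopsies. Use a log scale only if the count distribution calls for it.
- **The aim itself.** Regress marker change on percent SALT change at week 24, adjusted for baseline marker level and biopsy week. Report it with and without adjustment for arm. The adjusted result shows whether marker decline tracks regrowth within arms. The unadjusted result keeps the part that arises because treatment moves both, which is arguably part of what the aim seeks.
- **Skin and blood.** Report a rank correlation between changes in skin and blood CD8+NKG2D+ cells.
- **Other markers.** Apply the same approach to NKG2D-ligand and interferon-gene markers, and state how multiple markers are handled.
- **Schedule.** Reconcile the two biopsy schedules before the model is fixed, because they decide between one pair and repeated measures.

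The cost is plan wording and a little more analysis work. The analyses use samples already planned. The sponsor should expect modest precision: with complete data on 68 patients, only correlations of about 0.33 or more are detectable with 80% power.

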Despite the years of clinical experience of steroids in autoimmunity, the specific anti-inflammatory mechanisms are still incompletely understood.

It is thought that intralesional steroids act in alopecia areata by inhibition of the T cell mediated attack on the hair follicle. “Glucocorticoids exert their effects by binding to the glucocorticoid receptor (GR), a transcription factor capable of regulating many genes in a positive and or negative way”(12). The immunomodulatory action of glucocorticoids is thought to be due to its inhibitory role on the activity of transcription factors, such as activator protein-1 (AP-1) and nuclear factor κ β (NF κ β), that are involved in the activation of proinflammatory genes(13). Consequently, glucocorticoids suppress the production and effects of humoral factors involved in inflammatory responses and inhibit leukocytes’ migration to the inflammation sites”(14). While many patients benefit from intralesional steroids in AA, there is a group of patients that demonstrate a diminished response or resistance to this treatment modality.

The decreased expression of thioredoxin reductase 1 in the outer root sheath may be the cause for glucocorticoid resistance in some AA patients (15), (14). Specifically, Sawaya and Hordinsky reported that glucocorticoid receptor is inactive and cannot bind its ligand in cases of glucocorticoid resistant AA and further, that the activity of thioredoxin reductase 1 is significantly lower in glucocorticoid resistant AA. These findings indicate a possible role for thioredoxin reductase 1 in maintaining glucocorticoid sensitivity.

INNOVATION

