We will analyze the transcriptional expression signature of IFN-response genes in the skin and PMBC of drug-treated AA patients using qPCR as an indirect measure of efficacy. Signature genes have been selected based on their differential expression in affected vs. unaffected C3H mice, and on published studies on human AA patients vs. controls⁴⁰. The genes in the list represent mediators and effectors of the IFN response, which we found to be instrumental in disease pathology. Briefly, biopsies and peripheral blood from placebo control and treated patients will be collected at 0, 4, 12, and 24 week time points. Additional, optional scalp biopsies and peripheral blood may be taken at other time points in order to monitor response to therapy at the discretion of the investigator and with the consent of the study subject. RNA will be extracted from the tissues, and Sybr green based qPCR assays will be performed. Differential gene expression resulting from inhibitor treatment will be normalized to the expression of a housekeeping gene. We expect many of the genes on this list to revert to a basal level of expression, as compared in unaffected skin of an AA patient, or skin from a healthy control.

FUTURE PLANS AND INTEGRATION

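### The interferon-gene qPCR results depend on one unnamed housekeeping gene, and the plan has no check that treatment leaves it unchanged

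*Combined protocol and SAP*

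**What the plan says.** The qPCR work is described in Specific Aim 2, part iii (Analysis of Gene Expression by Quantitative RT-PCR). Its scope is stated as "We will analyze the transcriptional expression signature of IFN-response genes in the skin and PMBC of drug-treated AA patients using qPCR", and its role is "as an indirect measure of efficacy". On sampling, "biopsies and peripheral blood from placebo control and treated patients will be collected at 0, 4, 12, and 24 week time points". On the assay, "Sybr green based qPCR assays will be performed".

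The only normalisation rule in the documents follows: "Differential gene expression resulting from inhibitor treatment will be normalized to the expression of a housekeeping gene". It refers to one gene, which is not named. The stated expectation is: "We expect many of the genes on this list to revert to a basal level of expression", with unaffected skin of an AA patient or healthy-control skin as the benchmark. The instructions for processing blood and tissue samples standardise tissue handling before RNA extraction, but add nothing on normalisation.

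Two other sections bear on whether one reference is safe. Mechanism of action of intralesional steroids describes the glucocorticoid receptor as "a transcription factor capable of regulating many genes in a positive and or negative way". The Aim 2 rationale lists the changes to be correlated with treatment and disease status as "1) histological improvement; 2) reduced IFN responses; 3) reduced HF NKG2DL expression", followed by a decline in circulating and peribulbar CD8+NKG2D+ cells. Part ii then looks for resolution of the total cellular infiltrate.

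**The concern.** Normalising to one gene is valid only if treatment leaves that gene's share of the sample RNA unchanged. The protocol itself gives two reasons not to assume this in skin: the drug acts through a receptor that alters the expression of many genes, and the mix of cells contributing RNA to the biopsy is expected to change as infiltrate clears.

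Every signature gene has the same denominator, so an error in it does not average out across the signature. It moves all genes together in one direction. A rise in the reference would look like part of the hoped-for fall in interferon-response genes, and a drop in the reference would hide part of a real fall. Saline patients receive no drug, so a drug effect on the reference stays in the IL TAC versus saline difference.

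The normalisation sentence speaks of inhibitor treatment, and part ii of the same Aim refers to Jak1/Jak2 inhibition, whereas the study drug is triamcinolone. The rule may therefore have been written with another drug in mind. The point does not depend on that.

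**Working it through.** The plan states no figure for the qPCR analysis, so there is none to reproduce. The check is of the mechanism.

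**Inputs from the documents.** One reference gene; SYBR green qPCR; skin and PBMC; placebo and treated samples; about 17 subjects per arm, 68 in total (Sample size).

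**Inputs assumed, because the documents give none.** Reference shift d of 0.25 to 1 cycle; each cycle doubles the product; per-gene SD 0.5 or 1.0 cycle; reference SD 0.3 cycle; 20 signature genes that vary independently.

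**Step 1: one reference.** Normalised value = Ct(target) − Ct(reference). If reference expression rises by d cycles, Ct(reference) falls by d, the difference rises by d, and the apparent expression of every unchanged target is multiplied by 2^-d.

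**Step 2: three references.** The geometric mean of expression is the arithmetic mean of Ct. If one of three shifts by d, the factor is 2^(-d/3). If all three shift together, it is 2^-d again.

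| d (cycles) | One reference | Three, one shifts | Three, all shift |
|---|---|---|---|
| +0.25 | 0.84 | 0.94 | 0.84 |
| +0.5 | 0.71 | 0.89 | 0.71 |
| +1 | 0.50 | 0.79 | 0.50 |
| −0.5 | 1.41 | 1.12 | 1.41 |
| −1 | 2.00 | 1.26 | 2.00 |

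So a 0.5-cycle rise shows as a 29% fall (1 − 0.71) and a 1-cycle rise as a 50% fall. With three references of which one shifts by 1 cycle, the fall is 21% (1 − 0.79).

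**Step 3: effect on a test.** Simulation with no true change in any target: 17 versus 17, two-sided t-test at 0.05 on the mean signature score, 1000 runs. Ranges cover the two per-gene SDs.

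| d | One reference | Three, one shifts |
|---|---|---|
| 0 | 5–6% | 4% |
| 0.25 | 48–61% | 15–18% |
| 0.5 | 97–99% | 40–64% |
| 1 | 100% | 91–99% |

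These rates are illustrative. Independent genes make the mean score very precise. Correlated genes would make it less so and lower the rates.

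**Step 4: can a stability test clear a reference gene?** Take 51 IL TAC (3 × 17) versus 17 saline, a true 0.5-cycle shift, and a two-sided t-test at 0.05. Power is about 42% if the SD is 1 cycle and 94% if it is 0.5. The 95% interval half-width is about 2.0 × SD × √(1/51 + 1/17) = 2.0 × SD × 0.28, or 0.56 and 0.28 cycle. A non-significant result could therefore leave a material shift undetected.

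**The case against.** The strongest reply is that no defect has been shown. The gene is unnamed, and nothing in the documents says it responds to triamcinolone. The remark about many genes is general, and the same paragraph goes on to name AP-1, NF-κB and proinflammatory genes. The qPCR methods are offered as a brief summary, so the singular may be loose wording. All of this stands, and it is why the point is put as a risk.

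A reader might infer that the whole molecular conclusion of Aim 2 would rest on the normaliser. The documents do not support that. Of the four readouts in the rationale, only the reduced interferon response uses qPCR. H&E, immunofluorescence (including IFN-γ staining) and flow cytometry use no reference gene.

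A reader might also infer that a shifted reference would simply pass as return to basal level. That is too strong as well. The plan expects many genes, not all, to return, and judges them against unaffected or healthy skin. A common factor would not bring genes raised by different amounts each to its own basal level, and at d = 1 a gene already at basal level would appear at half of it. The benchmark gives some ability to tell the artefact from true reversion, but it is not a planned check on the reference.

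The argument is weaker for PBMC. The one cortisol result quoted under Clinical experience with IL TAC for AA shows a systemic effect that had recovered by day 3, whereas the planned on-treatment blood samples mostly fall about four weeks after an injection.

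Finally, more reference genes are not a cure: if tissue composition moves them together, averaging does little. That also stands, and it shapes the fix.

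**Conclusion.** The point holds as a cheap improvement to one secondary readout. The plan relies on a single unnamed, unchecked reference gene in a setting where its own text gives reason to doubt stability. If that gene moved by d cycles, every normalised gene would move by 2^-d.

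The direction and the common factor follow from the method of calculation. The sizes, 29% at 0.5 cycle and 50% at 1 cycle, rest wholly on assumed shifts, and the true shift may be zero. A reader might take the simulated error rates as the trial's error rate; they are not, because the shift, SDs, gene count and independence were all chosen for illustration.

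The SALT primary endpoint, sample size, alpha and safety analyses are unaffected.

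**What to change.** In Specific Aim 2, part iii:

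- Normalise on the log2 (delta-Ct) scale to the geometric mean of several reference genes (for example three) from different functional classes, named before any signature gene is analysed. If a single gene was only loose wording, naming the genes settles it.
- Using equal RNA input, report each reference gene's estimated change from baseline and its IL TAC versus saline difference, with confidence intervals, separately in skin and PBMC. Judge these against a tolerance set in advance, and do not keep or drop a gene on a non-significant test. Where the interval is wider than the tolerance, say that stability was not established.
- Repeat the signature analysis under each alternative reference as a sensitivity analysis.
- State that averaging reduces but does not remove the artefact, especially if tissue composition moves all the references together.
- Correct the reference to inhibitor treatment so that the sentence describes the study drug.

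The cost is a short wording change and, with three references, two more SYBR assays per sample: a little more RNA, plate space and reagent. The assays are meant to run on RNA already extracted. The documents give no RNA yield and mention budget constraints, so the laboratory should confirm that the 4 mm biopsies provide enough.
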